No preliminary studies have been carried out examining preoperative exercise in patients with pancreatic cancer. The preoperative exercise intervention, however, will be administered through the BFitBWell Cancer and Exercise Program at the Anschutz Health and Wellness Center. This program has successfully provided individualized exercise interventions to over 100 cancer survivors during the past two years. These interventions are led by trained cancer and exercise specialists, and have led to consistent improvements in physical fitness, physical function, and quality of life.

The BFitBWell program has provided exercise interventions for six patients with pancreatic cancer. Pre- and post-program measures of physical fitness were collected in two of these patients, both showing improvement. Measures of strength and physical function improved in the majority of patients and 4 of 6 patients reported measurable decreases in fatigue.

Based on discussions with physicians at the University of Colorado Cancer Center, approximately 100 patients are diagnosed and treated there each year who would be potential participants in the proposed study.

IV. Research Methods

A. Outcome Measure(s):

Physical fitness and function outcomes:

The primary outcome of physical fitness and function will be the *400-meter walk time*, which is a validated measure of cardiorespiratory fitness and mobility. The test assesses the time it takes a participant to independently walk 400 meters¹⁵. This test was developed to assess functional walking and exercise capacity in older adults, as distance was found to be more motivating than time (compared to the 6 minute walk test). This test has been associated with the development of cardiovascular disease and functional limitations¹⁶, and has been used to assess functional walking and exercise capacity in cancer populations¹⁷.

Secondary measures of physical fitness and function include:

Lean muscle mass and body composition. This will be assessed utilizing a dual-energy x-ray absorptiometry (DXA) scan. This is the gold standard measure of body composition and commonly used in studies of exercise interventions in cancer survivors¹⁸. The potential preservation of lean muscle is an important assessment in this population as improved muscle quantity and quality has been associated with improved postoperative outcomes in patients with pancreatic cancer undergoing surgery¹⁹.

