Gait speed is an easily implemented measure linked to a variety of functional outcomes in multiple populations²⁰. It will be measured during the middle 4 meters of a 10 meter course where participants will be instructed to walk at a normal pace and as quickly, but safely as possible. Participants will perform one practice trial and two test trials for each pace, with the fastest trial recorded, according to NIH guidelines²¹.

The *Timed Up and Go (TUG)* times participants as they rise from a chair, walk 3 meters, turn around, and return to the chair and sit²². One practice trial is performed, followed by two test trials. The two test trials are averaged for the final time. This is an easily implemented test that has shown good sensitivity and specificity for predicting falls in older cancer patients²³, as well as predicting surgical complications following cardiac and colorectal procedures²⁴.

The *Stair Climb Test (SCT)* records the time taken to ascend and descend a single flight of stairs. It correlates with the TUG²⁵, but as a higher level task, reduces possibilities of a ceiling effect during data processing and has been utilized in previous studies of cancer survivors¹⁸. One trial is performed.

The *Single Limb Stance (SLS)* test records how long participants can balance on one leg, with a cap at 30 seconds. Participants are given two attempts with the best time recorded. This is a valid and reliable measure of balance and postural stability²⁶.

The *30 sec Sit-to-Stand (30StS)* test is associated with strength and function of the lower extremities and records the number of times participants can go from a seated position to a standing position in 30 seconds²⁷. It is a valid and reliable test that has been used previously to assess strength and function in cancer survivors¹⁸.

Grip strength will be assessed on both the dominant and non-dominant hands using grip dynamometry. This is a valid and reliable measure²⁸ that has been associated with physical function, health, gross strength, and survival in cancer survivors²⁹.

Average daily step count (ADSC) will be assessed using pedometers. Pedometers will be given to participants for 7-day periods and participants will record their daily step count in a paper journal at the end of each day, prior to resetting the pedometer. Participants will also record any periods of time that the pedometer was not worn. *ADSC* will be assessed as average step count per day worn.

Postoperative outcomes:

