Assessments: All assessments will be performed at the Anschutz Health and Wellness Center. Participants will also complete the Godin Physical Activity Questionnaire during Visit 1 only. The following assessments will be completed at visits 1, 2, and 3.

A total body DXA scan will be performed to determine body composition. The scan takes approximately 3 minutes, but 15 minutes is allocated for data entry and positioning the patient.

HRV assessments will be performed prior to functional testing, to avoid the potential impact of physical activity on heart rate measures. This assessment will be performed in a private examination room and will take approximately 30 min.

Physical fitness and function assessments will then be performed. These assessments will be performed in the same order at every assessment, with the most fatiguing assessments performed at the end of the session. The order will be: SLS, TUG, grip strength, 30StS, SCT, gait speed, 400MWT. All tests will be performed by the same investigator at all time points.

This investigator is a licensed physical therapist with experience performing functional tests in medically involved or functionally limited populations. A secondary tester, blinded to participant group, will be present at all sessions to provide any necessary assistance and insure lack of testing bias. Participants will also be given the activity tracker to assess ADSC, with instructions on how to use the device and how to return the device in one week. The functional assessment period will take approximately 1 hour.

Questionnaire data will be collected using REDCap software. Participants will have two options for completing questionnaire data at each assessment: 1) completion of questionnaire data via emailed REDCap survey at the Health and Wellness Center via provided computer or tablet, 2) completion of printed questionnaires provided at the functional assessment. Data obtained from participants completing printed questionnaires will be entered in the REDCap system by two study investigators independently to insure accuracy, following which hardcopies will be destroyed.

If participants will not receive a standard blood draw as part of their medical care within a one-week window of the visit, they will be transported to the CTRC where the necessary blood draw will be performed.

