Thirty days after hospital discharge, the participants' electronic health record will be reviewed to retrieve data about initial hospital length of stay and 30-day unplanned hospital readmission. Visit 3 will be performed at approximately 6 weeks post hospital discharge. This is the time at which some patients may begin more chemotherapy or radiation treatment (adjuvant therapy), and Visit 3 will be performed prior to this to avoid confounding effects of the therapy.

Exercise Intervention: Participants will start the exercise program within four weeks of their diagnosis and decision to undergo neoadjuvant treatment and continue until surgery. Participants will continue to receive the standard medical care (described below) provided at UCCC. Individual exercise sessions in this program implement a "whole body" approach and consist of a 10-min cardiovascular warm-up and 50 minutes of cardiovascular endurance, resistance, and flexibility exercises (session components). Typical cardiovascular endurance exercises include walking on an indoor track or treadmill, stationary cycling, and stationary rowing. Resistance training includes exercises using body weight, free weights, and weight machines targeting increased strength of the large upper and lower extremity muscle groups and core stability. Flexibility exercises target major muscle groups activated during the exercise. Target intensity of exercise will be based on the American College of Sports Medicine (ACSM) recommendations for cancer survivors²: 40-85% heart rate reserve for cardiovascular endurance exercises; 60-70% one repetition maximum for resistance exercises; and a rate of perceived exertion of 12-16 on a 6-20 Borg scale for all activities.

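### The step-count week follows each visit, so the Visit 2 minus Visit 1 change may include supervised exercise sessions, days around the operation, or both

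*Combined protocol and SAP*

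**What the plan says.** Section IV.A (Outcome Measure(s)) lists ADSC under the heading "Secondary measures of physical fitness and function include". It states that "Pedometers will be given to participants for 7-day periods" and that ADSC "will be assessed as average step count per day worn". Participants write down each day's count in a paper journal, and "Participants will also record any periods of time that the pedometer was not worn".

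Section IV.C, under Assessments, applies this at every visit ("The following assessments will be completed at visits 1, 2, and 3"). Participants are "given the activity tracker to assess ADSC, with instructions on how to use the device and how to return the device in one week".

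On the exercise period, Section IV.C (Exercise Intervention) says: "Participants will start the exercise program within four weeks of their diagnosis and decision to undergo neoadjuvant treatment and continue until surgery". The Protocol paragraph of the same section describes Visit 1 as before the intervention, and Visit 2 as after the intervention and before surgery. Section IV.E adds that an extended gap between the end of exercise and surgery is to be avoided.

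Section IV.F defines change scores as Visit 2 minus Visit 1. It compares both baseline values and change scores between groups with exact permutation tests.

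**The concern.** The visit labels place the clinic tests before and after the intervention, but they do not place the step-count week. That week starts when the tracker is handed over. At Visit 1 it can overlap the first supervised sessions. At Visit 2 it can overlap the last sessions, the operation and the days after it.

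The two kinds of overlap act differently. Session steps arise only in the exercise group, because controls receive no exercise intervention. They can therefore produce or hide a between-group difference without any change in what participants do on their own. Surgery can fall in the Visit 2 week of either group, where it lowers the average or leaves fewer days behind it. A permutation test deals with chance and does not remove either effect. The covariates proposed in Section IV.E (duration of exercise and of neoadjuvant therapy) do not address them either.

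What is at stake is whether a change in ADSC, or a baseline difference in it, can be read unambiguously as a change or difference in habitual activity.

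**Working it through.** The plan gives no step-count assumption, so there is no stated figure to reproduce. The check sets the timing statements side by side and then illustrates the size.

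**1. Position of the wear week.** Hand-out at the visit, return one week later and a 7-day wear period together give a week that follows the visit.

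**2. Visit 1 week.** The clinic visit precedes the intervention, but no minimum interval to the first session is stated. Eligibility (Section IV.B) allows up to four weeks since diagnosis, and exercise starts within four weeks of diagnosis and the treatment decision. If that window is counted from diagnosis, a participant whose Visit 1 falls in the fourth week has less than 7 days left in it, so a full session-free week does not fit.

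**3. Visit 2 week.** There are two readings:
- Exercise runs up to surgery (Exercise Intervention). The seven days after a preoperative visit then lie in the exercise period, reach the operation, or both.
- Exercise has ended by Visit 2 (Protocol paragraph). Sessions are then absent, but surgery is meant to follow without an extended gap and may fall inside the week.

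Neither reading protects the week in the text.

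**4. What is counted.** The average is over days worn. No text excludes session steps, session days or postoperative days. Unworn hospital days drop out; worn ones do not.

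**5. Size of the session effect (illustration).** From the documents: three sessions a week are encouraged, and sessions typically include track or treadmill walking. Assumed, not in the documents: 10 to 30 walking minutes per session at 80 to 120 steps per minute.

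Added steps per day = sessions × minutes × cadence / 7
- Three sessions, low: 3 × 10 × 80 / 7 = 343
- Three sessions, high: 3 × 30 × 120 / 7 = 1,543
- One session, low: 1 × 10 × 80 / 7 = 114
- One session, high: 1 × 30 × 120 / 7 = 514

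If sessions fall only in the Visit 2 week, the exercise group's change rises by this amount. If they fall only in the Visit 1 week, it falls by this amount. If both weeks are equally exposed, the effect cancels.

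**6. Size of the surgery effect (illustration).** Assumed: 5,000 steps per day on three preoperative days, and 0 to 500 on four worn postoperative days.
- (3 × 5,000 + 4 × 0) / 7 = 2,143
- (3 × 5,000 + 4 × 500) / 7 = 2,429

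If the four postoperative days are not worn, ADSC stays at 5,000 but rests on three days.

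**The case against.** The strongest reply is that the needed timing may be in Figure 1, which is described as placing visits and intervention relative to diagnosis and surgery and is not shown in the copy reviewed. Section IV.E also rules out only a long gap before surgery, so a short session-free week is compatible with the plan. The same section gives a typical 16 weeks of neoadjuvant therapy and 12 of exercise; the difference of 4 weeks leaves room for a clean week, although it is not assigned to one. All of this stands, and it is why the conclusion is that the weeks may be contaminated.

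Four stronger readings are tempting and are not supported:
- **That the Visit 2 week must contain sessions or the operation.** This follows only if exercise literally runs up to surgery, and the label given to Visit 2 says otherwise.
- **That the change score measures the intervention itself.** Only session steps have that character. Surgery is not the intervention and can affect either group. Sessions may also add few steps, since cycling, rowing, resistance and flexibility work are listed too.
- **That the result cannot be read as function at all.** Total steps, sessions included, is a legitimate measure of activity. Whether to include them is a choice of estimand that the plan should state.
- **That Visit 3 shares the problem to the same degree.** Its wear week could run into adjuvant therapy although "Visit 3 will be performed prior to this to avoid confounding effects of the therapy". But Visit 3 is outside the change score, feeds only a descriptive trajectory, and only some patients may start such therapy then.

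**Conclusion.** The concern holds in limited form. Followed as written, the hand-out rule puts the step-count week after the visit, and the text does not keep sessions out of the Visit 1 week or sessions and surgery out of the Visit 2 week. The Visit 2 minus Visit 1 change in ADSC is therefore open to a session artefact in exercisers of roughly 100 to 1,500 steps per day, in either direction or cancelling, and to a lowered or shortened Visit 2 week in either group. These sizes rest on assumed walking minutes, cadence and background steps; the documents give none. The conclusion about timing rests on the text alone, and Figure 1 could narrow it.

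The consequence is small. ADSC is one of several secondary measures in a non-randomized pilot of 30. The 400-meter walk, length of stay, readmission and the feasibility outcomes are untouched.

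**What to change.** 1. Reconcile the description of Visit 2 as after the intervention with the statement that exercise runs until surgery, and state where each wear week sits relative to the first session, the last session and the operation.
2. For baseline, count only days before the first exercise session. Issue the tracker at familiarization where that is a separate occasion.
3. Have the Visit 2 week end at or before Visit 2, so that no postoperative day counts. This removes surgery but not sessions, so step 4 is also needed.
4. Match the daily step journal to the session log, both already collected, and report ADSC on non-session days alongside total ADSC, with the number of days behind each average.

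Removing the tracker during sessions is not recommended. It would impose non-wear on exercisers only, while the per-day-worn denominator would still count those days.

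The cost is scheduling text, earlier hand-out or mailing of trackers, and fewer usable days for some participants, notably those who combine familiarization with Visit 1. Sessions typically take place Monday to Friday. With three session days, an exerciser's non-session days would be 2 weekend days out of 4, against 2 out of 7 in a full control week, so the non-session figure should be read beside the total and not in place of it.

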Heart rate variability (HRV) will be used as an objective measure of stress, both physiologic and psychological. HRV will be assessed in four different conditions. Electrocardiography (ECG) will be recorded during a 10 minute baseline period (seated), a 5 minute orthostatic challenge (sit-to-stand), a 5 minute cognitive dissonance period (standard Stroop Task), and a 5 minute cancer-salient dissonance period (cancer-related Stroop Task)³⁵. The standard Stroop Task involves naming the color a word is printed in. The words are usually a color word (e.g. "Red", "Blue") and sometimes do not match the color the word is printed in. The cancer-related Stroop Task also requires participants to name the color a word is printed in, except words will either be neutral words or words related to cancer (e.g. "Malignancy", "Chemo"). Participants will be told prior to performing either task that the tasks are designed to be challenging and possibly evoke emotion. The standard Stroop and cancer-related Stroop will be performed in a random order between participants, but kept constant across Visits within participants, and separated by a 5 min rest period. Both time and frequency domain HRV measures will be calculated from the ECG signal for each period offline, quantifying overall autonomic tone (assessed by average heart rate and the total spectral power of HRV), parasympathetic tone (the high frequency component of HRV), and changes from baseline for each condition.

Biomarker Assessment:

Systemic markers of inflammatory status will be assessed by measuring pro-inflammatory cytokines: serum C-reactive protein, associated with postoperative outcomes in patients with pancreatic cancer³⁶, interleukin-6, potentially involved in the development and progression of cachexia³⁷, and soluble tumor-necrosis factor receptor 1, a possible indicator of exercise-induced changes in systemic inflammatory status³⁸, and an anti-inflammatory cytokine, interleukin-10, involved in exercise-induced pathways³⁹. Blood samples will be drawn at the same time as other blood draws performed as part of standard care at the University of Colorado Cancer Center, to reduce patient burden. If these routine blood draws do not occur within a one week window of the assessment, blood draws will be performed at the Clinical and Translational Research Center on the Anschutz Medical Campus, where all sample analyses will be performed.

B. Description of Population to be Enrolled

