Recruitment: Participants will be recruited from the University Hospital Cancer Center. Patients with a recent diagnosis (< 4 weeks) of pancreatic cancer will be given information on the study by their treating physicians and asked if they would be interested in participating. If yes, physicians will have patients complete a HIPAA A form to provide study personnel with their name. Study personnel will access the patients' medical records to evaluate the inclusion/exclusion criteria. If these criteria are met, research personnel will meet with the

potential participant at the University of Colorado Cancer Center to provide information about the study. If patients are still interested in participating, the familiarization and possibly first visit will be scheduled. Participants will have the option of combining the familiarization session and Visit 1. All data collected during screening will be destroyed and recollected after obtaining written consent in patients choosing to participate. If the inclusion/exclusion criteria are not met after review of the health record, the patient will be contacted and the exclusion decision will be explained.

Group Assignment: Volunteers meeting the inclusion and exclusion criteria and willing to participate in the exercise intervention will be assigned to the exercise group. The standard of care, non-exercise control group will comprise volunteers who meet the inclusion and exclusion criteria but are unable to commit to participation in the exercise intervention for practical reasons (e.g. barriers in transportation or home location). The use of a non-randomized study design is to maximize patients participating in the exercise program to determine accrual rate, program adherence, and safety while still allowing a non-exercise control group.

Protocol:

[figure not shown]

Figure 1

Figure 1 shows the event timeline of the study, with time points of visits and intervention in relation to diagnosis and surgery. Written informed consent will be obtained by a study investigator during a familiarization period, where participants will have assessments and the exercise investigation explained in-depth. There will be four time points for data collection: pre-intervention (Visit 1), post-intervention and preoperative (Visit 2), 30-day postoperative (data retrieved from electronic health record), and follow-up (Visit 3).

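### The practical barriers that place people in the control group can also keep them from the on-site visits, and as written even the emailed questionnaire offers no remote route

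*Combined protocol and SAP*

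**What the plan says.** Allocation is not random. Under IV.C, Group Assignment, those willing to exercise form the exercise group. The controls are eligible volunteers who "are unable to commit to participation in the exercise intervention for practical reasons (e.g. barriers in transportation or home location".

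Under IV.C, Assessments: "All assessments will be performed at the Anschutz Health and Wellness Center". DXA, heart rate variability, the functional tests and the questionnaires are due at Visits 1, 2 and 3. There are two questionnaire routes. The first is "completion of questionnaire data via emailed REDCap survey at the Health and Wellness Center via provided computer or tablet". The second is "completion of printed questionnaires provided at the functional assessment".

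The exercise sessions are held at the same centre. Participants are encouraged to attend three times a week for at least eight weeks (IV.C, Exercise Adaptations).

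The Data Analysis Plan (IV.F) defines the change score as Visit 2 against Visit 1 and compares groups by permutation test. It gives no method for missing data. Section IV.E concedes that selection into groups may bias results and unbalance baselines, but does not mention unequal loss to follow-up. The sample size paragraph (IV.B) adds the same 3 participants to each group for attrition.

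**The concern.** The only reasons the plan names for being a control concern getting to the exercise centre, and that is also where follow-up is measured. Exercisers who keep to the programme are there several times a week until surgery, so Visit 2 adds little travel for them. For a control it is a separate trip.

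A control who does not make that trip has no Visit 2 value. That removes the change score for the primary fitness outcome (400-metre walk time), the other functional tests, body composition, heart rate variability, fatigue, quality of life, perceived stress and depression. A missed Visit 3 removes the participant's last point from the descriptive trajectory.

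For the four repeated questionnaires the loss is largely avoidable. A survey that can be emailed already exists, but the text ties its completion to the centre.

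What is at stake is that completeness may depend on group through the way the groups are formed. Adjusting for baseline covariates does not restore a missing change score.

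**Working it through.** **1. Which outcomes depend on attending.**

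| Outcome | Source in the protocol | If the visit is missed |
|---|---|---|
| 400-metre walk, other functional tests, DXA, heart rate variability | IV.C, Assessments: on site | Lost |
| Fatigue, quality of life, perceived stress, depression | IV.C, Assessments: on-site device, or paper given out there | Lost; no other route is stated |
| Step count | IV.A: "Pedometers will be given to participants for 7-day periods and participants will record their daily step count in a paper journal" | Recorded away from the centre, but the device is issued at the visit |
| Blood markers | IV.A: "Blood samples will be drawn at the same time as other blood draws performed as part of standard care" | Kept if a routine draw falls within one week |
| Length of stay, readmission | IV.C: "electronic health record will be reviewed to retrieve data about initial hospital length of stay and 30-day unplanned hospital readmission" | Kept |

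The text does not say whether the printed forms may be taken home. A participant who does not attend never receives them, so paper does not help when a visit is missed.

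**2. The plan's own sample size figure.** Inputs from IV.B: difference 4 days, SD 3, α = 0.05 (taken as two-sided), and 0.90 read as power.

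n per group = 2 × [3 × (1.960 + 1.282) / 4]² = 11.82, rounded up to 12.

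The plan's 12 is reproduced. It is for length of stay, which comes from the health record. The allowance of 3 in 15 (20%) is the same in both groups, and the cited 28% attrition is an overall figure. Nothing here sizes loss by group for visit-based outcomes.

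**3. Can the direction of bias be settled?** Let a fraction p of a group miss the visit, and let a participant's standardised change correlate r with the tendency to attend. Under a bivariate normal model the mean change among attenders shifts by

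r × φ(Φ⁻¹(p)) / (1 − p).

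The documents give neither p nor r. Assume 20% loss in exercisers, 40% in controls, and r from 0.3 to 0.7.

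- Exercisers (p = 0.20): shift 0.105 to 0.245 SD.
- Controls (p = 0.40), same r: shift 0.193 to 0.451 SD.
- Net with equal r: 0.193 − 0.105 = 0.088 to 0.451 − 0.245 = 0.206 SD against exercise.
- Net if control loss is purely logistic (r = 0 in controls, unchanged in exercisers): 0.105 to 0.245 SD in favour of exercise.

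The sign changes with an assumption on which the documents are silent.

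**4. Would a test of attrition reassure?** With an assumed 3 of 15 exercisers and 6 of 15 controls lost, Fisher's exact test gives p = 0.43. At this size a doubling of loss would pass as non-significant, so counts and reasons by group say more than a p-value.

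**The case against.** The strongest reply is that being unable to commit to exercise is not the same as being unable to attend an assessment. The programme asks for 3 × 8 = 24 or more trips; follow-up asks for two. Controls complete Visit 1 at the same centre and have the assessments explained at consent. They receive their treatment and surgery at the cancer center and are paid $50 per completed visit. Transport and home location are examples, not the definition of the group. Exercisers may also leave because of programme burden, and under Data Safety and Monitoring (IV.D) a participant judged physically incapable of the intervention or the assessments is discontinued. All of this stands. It reduces the risk to an unknown degree, but it does not give a participant who misses a visit any way to return a questionnaire.

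A reader might also infer four stronger things that the documents do not support.

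- That every follow-up outcome is exposed, or that controls will certainly lose more. The table above shows the exceptions, and certain loss is a prediction.
- That the exercise effect is therefore understated. This needs control loss to be related to health. If it is mainly about distance, the result can go the other way.
- That evaluable controls may fall below the required 12, with a loss of power. That number belongs to length of stay, which missed visits do not remove. The plan makes no power claim for change scores.
- That Visits 2 and 3 should be required on the same day as clinic attendances. The listed assessments take about 1¾ hours (15 min DXA, 30 min heart rate variability, 1 hour function), and a treatment or clinic day could itself affect heart rate variability, fatigue and walking.

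**Conclusion.** The concern holds in a limited form. The plan sets up a link between how controls are chosen and how easily they can be measured, closes the one remote route that its existing survey could offer, and does not address the resulting risk. The exposure covers the four repeated questionnaires, DXA, heart rate variability and the functional tests, in a group of 15 out of 30 (50%). Step counts are partly exposed, through issue of the device.

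The amount of unequal loss and the direction of any bias cannot be determined from the documents; the shifts in step 3 of the working rest on assumed rates and show only that the direction is open. The conclusion assumes that the questionnaire wording is meant literally and that no unwritten practice lets participants complete forms at home. It does not extend to length of stay, readmission or blood taken at routine draws. It is a worthwhile improvement because it is cheap, not because a large bias has been shown.

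**What to change.** In IV.C, Assessments, remove from questionnaire option 1 the requirement to complete the emailed survey at the centre on a provided device. State instead that participants in both groups may complete it from any location within the visit window, including when the on-site visit is missed; a device can remain available for those who attend. Define that window. It should close before surgery for Visit 2 and before any adjuvant therapy for Visit 3, in line with how the protocol already places those visits. Record where each questionnaire was completed.

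In IV.F, add that Visit 2 and Visit 3 completion, with reasons for loss, will be reported by group beside each change-score result.

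The cost is a change of protocol wording, one extra data field and a short reporting table. The survey platform is already in use. The downside is a mixture of home and on-site completion, which the location field makes visible. The change does nothing for the 400-metre walk or the other on-site tests; for those, reporting by group shows the loss but does not prevent it.
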